4.1 Screening for Eligibility and Consent

All women with singleton gestation presenting for prenatal care before approximately 24 weeks gestational age are potentially eligible for screening. Women, who are identified with a short cervix through clinical or research screening will be approached for inclusion into this trial. The measurement must have been made by a certified sonographer. Patients who have had a documented short cervical length (≤ 20 mm) by non-study certified personnel are eligible for inclusion in the study but would still have to undergo cervical length screening by an official study sonographer.

If the cervical length is 20 mm or less, consent for the trial will be obtained and the patient will be screened for eligibility. If an obstetrical ultrasound examination to evaluate the fetus for anomalies has not been performed at 14 weeks of gestation or later, one must be performed before randomization. The results of this ultrasound must be reviewed to check for exclusion criteria, and if it is the patient's first ultrasound with dating parameters, gestational age. The results of the dating and/or anatomy ultrasounds may be made available to the patient's physician.

Immediately prior to randomization a speculum examination will be performed (followed by a digital exam if necessary) to rule out cervical dilation and cervical infection, as well as an evaluation of preterm premature rupture of the membranes (pooling, nitrazine, ferning). A cervicovaginal fluid sample, vaginal Gram stain, and vaginal pH will be collected to assess for local inflammation and vaginitis.

4.2 Randomization

Eligible and consenting patients will be randomized by certified research staff using an internet based randomization system maintained by the BCC. The patient will be assigned either to pessary or usual care.

4.3 Baseline Procedures

In addition to information collected for eligibility, project gestational age, and project EDC determination, the following information will be obtained at randomization from a patient interview followed by a review of her chart:

- Demographic information: age, race, insurance status
- Medical history: pre-pregnancy weight, current weight, height, chronic disease history
- Obstetrical history including outcome of all prior pregnancies and history of vaginal bleeding in the current pregnancy
- Social history: marital status, years of education, alcohol use, tobacco use and other maternal drug use
- Complications during this pregnancy including sexually transmitted infections and vaginal infections.
- Current and planned progesterone treatment per usual care at the participating site.

Women randomized to pessary will be evaluated by an accredited obstetric care provider (nurse, nurse practitioner, nurse midwife, or physician) who has been trained in the proper technique of pessary sizing and placement. The provider will fit the patient for and place an Arabin pessary according to standard techniques so that it encircles the cervix and rests in the anterior and posterior fornices. Care to ensure

that the entirety of the cervix is contained within the pessary will be assessed through a vaginal digital examination. Women will be provided with written education regarding anticipated symptoms with a pessary and indications for physician assessment. The patient will be instructed to present to the research center on the next business day if the pessary should be spontaneously expelled.

All women will be provided with education regarding the warning symptoms of preterm labor.

4.4 Patient Management and Follow-up

All patients will receive a phone call from a research nurse to assess compliance and symptoms within one week of randomization. If a patient in the pessary group is experiencing discomfort she will be asked to come in to assess the pessary for fit and possible replacement with a different size.

All patients will have monthly study visits (in-person or virtual) with a research nurse/provider for compliance, symptoms related to treatment, review of recent hospitalization(s), and any additional treatment received for preterm labor, such as corticosteroids or tocolytics since their last visit. Data on ongoing progesterone treatment will be collected.

A second set of cervicovaginal fluid samples will be collected if an in-person study visit occurs between 24 to 32 weeks by project gestational age. The second samples will include a cervicovaginal fluid sample, vaginal Gram stain and vaginal pH (without a speculum exam) to assess for local inflammation and vaginitis. The samples will be evaluated not only for their potential individual association with outcomes, but also to examine any potential interval changes that may be associated with the assigned treatment arm. Women randomized to pessary will have at least one in-person visit to undergo a digital examination to ensure appropriate pessary placement.

At the second study visit after randomization, patients randomized to pessary will be asked to complete a questionnaire summarizing their experience with the pessary. The questionnaire will be administered again at 37 weeks gestation.

Therapy will be continued until 36 weeks 6 days, at which time all patients should have a final study visit scheduled. Women in the pessary arm will have the device removed at this visit.

The pessary may be removed as necessary to evaluate vaginal bleeding contractions, preterm labor, or other conditions. The pessary will be reinserted if symptoms resolve and the cervix is less than 3 cm dilated. A patient will be instructed to call if the pessary comes out (fully or partially), becomes dislodged or if she removes it herself so that arrangements for a replacement pessary can be made. If the patient is uncomfortable, a replacement pessary may be inserted or the original pessary may be reinserted or repositioned.

Indications for pessary removal are as follows:

1. Painful, regular uterine contractions occurring at least every 10 minutes in order to facilitate accurate assessment of cervical dilation and effacement, especially if cervical examination with the pessary in place suggests dilation or progressive cervical shortening.
2. Confirmed rupture of membranes — the initial assessment for rupture can be performed with the pessary in place, but once confirmed, the pessary should be removed.
3. Confirmed diagnosis of clinical chorioamnionitis.
4. Active vaginal bleeding greater than spotting — if the bleeding ceases and there are no other contraindications, the pessary can be replaced.
5. Development of significant cervical edema with a cervical herpetic lesion.
6. Cervical laceration or significant edema.

7. At the patient's request because of significant discomfort or other reasons.

If a patient presents with symptoms of vaginitis, she should be treated as per local clinical standards. No attempt will be made to alter or mandate clinical management of the subjects, which includes corticosteroids, tocolytics and magnesium sulfate. In rare instances an exam-indicated rescue cerclage may be placed at the discretion of the provider. Sexual intercourse is not expressly prohibited in this study. However, the use of serial cervical length ultrasounds, prophylactic tocolytic drugs or cerclage is discouraged.

Neonates will be followed to 28 days after the expected date of delivery or to discharge, whichever is longer. Maternal and neonatal records will be reviewed and a follow-up telephone interview conducted to capture neonatal and maternal outcomes.

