2.6 Safety and Acceptability of the Arabin Pessary

In the PECEP trial, 192 women were treated with the Arabin pessary.²⁶ While all women reported an increase in the amount of vaginal discharge, there were no serious adverse effects associated with the use of the pessary, including no increase in infection, rupture of membranes, or need for removal due to discomfort. Only 14% of patients required pessary repositioning at any point during pregnancy and only one patient (0.5%) requested pessary removal. There was no increase in the occurrence of adverse neonatal outcomes.

In the trial by Nicolaides et al., the pessary group had a higher rate than the control group of increased or new vaginal discharge (46.8% vs. 13.8%, $P < 0.001$) and pelvic discomfort (11.4% vs. 3.4%, $P < 0.001$). Ten percent (47 women) asked for the pessary to be removed, approximately half (25) because of discomfort and the remainder because of discharge (19) and vaginal bleeding (3). There appeared to be no provision in the protocol for replacing or repositioning the pessary. There was no difference in vaginal infection between the groups.²⁷

In the Hong Kong trial, 53 women were treated with the Arabin pessary.²⁸ Women in the pessary group experienced significantly more side effects (55.6% versus 27.3%) than in the expectant management group. Nearly all of the side effects reported were vaginal discharge and this accounted for the difference between the groups (25 women versus 12). There were no differences in vaginal infection, ruptured membranes or adverse neonatal outcomes. The pessary dislodged in 2 patients and required replacement.

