3.3 Design Summary

The study is an unblinded randomized controlled multi-center clinical trial of 850 women with a singleton gestation and ultrasound evidence of short cervical length, defined as less than or equal to 20 mm, randomized to one of two arms at participating MFMU Network clinical centers.

- Usual care. Women will receive vaginal progesterone if they meet the criteria per local standard of care.
- Arabin cervical pessary. If the local usual care is to receive vaginal progesterone for a short cervix, women randomized to the pessary will also receive progesterone.

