4.6.2 Maternal Secondary Outcomes

1. Interval from randomization to delivery or fetal demise
2. Gestational age at delivery
3. Preterm delivery or fetal demise prior to 28 weeks, 32 weeks or 35 weeks
4. Preterm premature rupture of membranes (pPROM)
5. Spontaneous preterm delivery (following preterm labor or pPROM)
6. Indicated preterm delivery

7. Cesarean delivery
8. Chorioamnionitis
9. Maternal antepartum hospitalization days
10. Maternal antibiotic or antifungal use for vaginal infection
11. Vaginal infection as assessed by local clinical diagnosis
12. Treatment for preterm labor, including cervical cerclage
13. Side effects including symptomatic vaginal discharge or discomfort
14. Discontinuation of pessary treatment and reason

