6.1 Data Collection Forms

Data will be collected on standardized forms on which nearly all responses have been pre-coded. Each form is briefly described below:

- TO01 Screening Log.
- TO01A Eligibility Checklist
- TO02 Eligibility and Randomization Form is completed for all patients eligible for the study.
- TO03A Pessary Accountability Log lists the specific pessary(ies) given to each patient.
- TO04 Baseline Form is completed for all randomized patients. This form includes detailed demographic and social data, medical and obstetrical history, and current pregnancy complications.
- TO04A Previous Pregnancy Outcome Form.
- TO05 Study Visit Form documents monthly study visits, possible side effects and compliance
- TO07 Unscheduled Visit or Hospitalization Form is completed for all patients who had an unscheduled emergency room, Labor & Delivery, clinic visit or hospitalization between the scheduled monthly visits, including the delivery admission.
- TO08 Maternal Delivery and Outcome Form documents specific pregnancy complications since randomization, in addition to labor, delivery and postpartum information.
- TO09 Neonatal Baseline Form records date and time of birth, delivery data and status at delivery, for each fetus/infant.
- TO10 Neonatal Outcome Form records outcome data for all infants admitted to the NICU or special care nursery.
- TO11 Patient Status Form documents loss to follow up/withdrawal status, last date of contact for lost to follow-up patients, side effects since the last dose.
- TO12 Adverse Event Form records serious and non-serious adverse events.
- TO13A Women's Views on the Arabin Pessary, a patient questionnaire.
- TO14 Pessary Removal Form documents the position of the pessary at the time of removal.

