Appendix A Design Summary

A Randomized Trial of Pessary in Singleton Pregnancies with a Short Cervix

OBJECTIVE: To determine whether pessary reduces the risk of preterm birth in women with a singleton gestation and a short cervix.

ORGANIZATION

Clinical Centers: Magee, UAB, Ohio State, Utah, Brown, Columbia, Case Western, UT-Houston, UNC, Northwestern, UTMB-Galveston, UPenn
 Subcommittee: [name] (Chair)

DESIGN

Major Eligibility Criteria: ❖ Singleton gestation
 ❖ Gestational age 16⁰ to 23⁶ wks
 ❖ Cervical length ≤ 20.0 mm

Groups: ❖ Usual Care (may include vaginal progesterone)
 ❖ Arabin Pessary + Usual Care

Random Allocation: Standard urn design; 1:1 allocation

Level of Masking: Unmasked

Stratification: ❖ Clinical site

Sample Size: ❖ 850

Assumptions: ❖ Outcome event=delivery < 37⁰ weeks gestation or fetal loss
 ❖ Usual care group event rate =28%
 ❖ Pessary group event rate =18.67% (33.3% reduction)
 ❖ Type I error = 2.5% (two sided with one comparison)
 ❖ Power =90%

Interim Analysis: ❖ Lan-DeMets group sequential method

SCHEDULED EVALUATIONS / DATA COLLECTION

Pre-Randomization: ❖ Cervical length measurement by trained sonographer
 ❖ Pregnancy, exposure and medical history

Randomization: ❖ Vaginal sample, vaginal Gram stain and vaginal pH

Post-randomization: ❖ Phone call to assess patient symptoms and compliance within 7 days of randomization
 ❖ Every four weeks: study visit to assess symptoms and compliance
 ❖ Study visit between 24 and 32wks: vaginal sample, vaginal Gram stain and vaginal pH
 ❖ Digital exam to ensure appropriate pessary placement (pessary group)

Delivery: ❖ Patient questionnaire 8 weeks after randomization and again at 37 wks gestation.
 ❖ Pessary group: assessed for fit or replacement, as needed
 ❖ Delivery and neonatal data

MANAGEMENT PROTOCOL

Both Groups: ❖ Vaginal progesterone per usual care and rescue cerclage if needed

Pessary Group: ❖ Placement management from randomization to < 37 wks

OUTCOME MEASURES

Primary: ❖ Delivery or fetal loss prior to 37 wks

Secondary: ❖ Randomization to delivery interval
 ❖ Gestational age at delivery
 ❖ Neonatal morbidity and mortality
 ❖ Lower genital tract or urinary tract infection
 ❖ Physician interventions including bedrest, cerclage, labor inhibition therapy

TIMETABLE

Enrollment: ❖ September 2016 to October 2019
 Data Collection: ❖ September 2016 to October 2019
 Closeout/Analysis: ❖ October 2019 to September 2021

References

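### Section 4.4 ties monthly symptom collection to treatment while Appendix A does not; applied literally, it could under-record usual-care symptoms and overstate the pessary's side effects

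*Combined protocol and SAP*

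**What the plan says.** Section 4.4 describes the first contact after randomization without any condition on cause: "All patients will receive a phone call from a research nurse to assess compliance and symptoms within one week of randomization". The visits that follow are described differently: "All patients will have monthly study visits (in-person or virtual) with a research nurse/provider for compliance, symptoms related to treatment". Appendix A describes those same visits again, this time without the link to treatment: "Every four weeks: study visit to assess symptoms and compliance".

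In section 6.1, the monthly visit form (TO05) is said to hold possible side effects and compliance. The patient status form (TO11) is said to hold "last date of contact for lost to follow-up patients, side effects since the last dose".

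The outcome that depends on this is maternal secondary outcome 13 in section 4.6.2: "Side effects including symptomatic vaginal discharge or discomfort". It has no relatedness condition and is not limited to pessary users. Section 3.2 asks whether the pessary, against usual care, changes any of the listed secondary outcomes, so outcome 13 is a comparison between arms.

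Section 3.3 makes the trial unblinded and says of usual care: "Women will receive vaginal progesterone if they meet the criteria per local standard of care". Section 4.3, in the paragraph on pessary fitting, adds: "Women will be provided with written education regarding anticipated symptoms with a pessary and indications for physician assessment". The only education it describes for every woman concerns the warning signs of preterm labor.

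**The concern.** A pessary user always has a treatment to which discharge or discomfort can be ascribed, including discharge she would have had anyway. A usual-care woman without progesterone has none, and section 4.4 does not say what treatment means for her. If staff who know the arm take the wording literally, her symptom has nothing to be related to and may not be recorded. Background symptoms would then count in full in one arm and only in part in the other, and the error would run against the pessary.

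Tolerability is part of the trial's case for the device (section 2.7), and section 2.6 shows that discharge and discomfort are its main known drawbacks. That section also shows that control women report these symptoms, so there is a background to lose.

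**Working it through.** The plan gives no figure for the side-effect comparison, so there is none to reproduce. The check sets the passages side by side and then works out how large the effect could be.

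**1. The passages**

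| Place | Who | Symptoms tied to treatment? |
|---|---|---|
| 4.4, one-week call | all | no |
| 4.4, monthly visit | all | yes |
| Appendix A, four-weekly visit | not limited to one arm | no |
| 6.1, TO05 | not limited to one arm | speaks of possible side effects; no relatedness judgement stated |
| 4.6.2, outcome 13 | not limited to one arm | no relatedness condition, but speaks of side effects |

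The second and third rows describe the same visit and disagree. No passage says which governs, and none requires the same questions in both arms.

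**2. Inputs**

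- Discharge in the international trial (2.6): 46.8% pessary, 13.8% control.
- Pelvic discomfort in the same trial: 11.4% and 3.4%.
- Any side effect in the Hong Kong trial (2.6): 55.6% and 27.3%.
- Share s of usual-care women without progesterone: not given. Assumed 10%, 25% and 50%.
- Arm size: 850 / 2 = 425.

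**3. Upper bound on the distortion**

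Suppose every symptom in untreated usual-care women is missed, none is missed elsewhere, and background rates do not depend on progesterone. With control rate c and pessary rate p:

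recorded control rate = c × (1 − s); recorded relative risk (RR) = p / [c × (1 − s)].

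For discharge at s = 10%: 0.138 × 0.90 = 0.1242, and 0.468 / 0.1242 = 3.77.

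| Symptom | True RR | s = 10% | s = 25% | s = 50% |
|---|---|---|---|---|
| Discharge | 3.39 | 3.77 | 4.52 | 6.78 |
| Discomfort | 3.35 | 3.73 | 4.47 | 6.71 |
| Any side effect | 2.04 | 2.26 | 2.72 | 4.07 |

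As risk differences, discharge goes from 33.0 points to 34.4, 36.5 and 39.9. Any side effect goes from 28.3 to 31.0, 35.1 and 42.0.

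**4. Partial application**

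If a fraction e of those symptoms is missed, replace s by s × e. With s = 50% and e = 50%, s × e = 25% and the discharge RR is 4.52. With s = 10% and e = 50%, s × e = 5% and it is 3.39 / 0.95 = 3.57. With e = 0 there is no distortion.

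**5. No true difference (illustration only)**

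Suppose both arms have true rate c. A two-sided 5% test of c against c × (1 − s), with 425 per arm, is significant with probability about 9%, 34% and 91% at s = 10%, 25% and 50% for c = 13.8%. For c = 27.3% the figures are about 15%, 65% and over 99%.

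**The case against.** The strongest reply is that section 4.4 lists topics for a visit. It does not say that unrelated symptoms are to be left out, and the phrase may simply name a kind of symptom, as distinct from hospital stays and preterm-labor treatment. The one-week call, Appendix A, TO05 and outcome 13 carry no explicit relatedness condition. Section 6.1 says the forms are standardized and mostly pre-coded, and section 1.3 refers to a manual of operations. Neither the form items nor the manual is in the documents, so a uniform checklist may already exist. This stands: a reader might infer that the visits record nothing but treatment-related symptoms and that the comparison is biased, and the documents do not support either statement.

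A reader might also infer that the trial could show a side-effect excess where none exists. Step 5 gives the arithmetic, but its premise conflicts with section 2.6, where discharge was more common with the pessary in the international and Hong Kong trials and all treated women in the Spanish trial reported more of it. The realistic risk is an exaggerated excess.

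The high end of the range is also doubtful. Section 2.3 says many obstetricians have adopted progesterone for a short cervix, section 5.2 calls the comparator the progesterone arm, and section 3.2 treats the pessary as an adjunct to progesterone. Against that, sections 3.3 and Appendix A leave progesterone to local practice, and section 5.5 lists it as a subgroup factor, so some untreated women are expected.

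TO11 is weak evidence. It records loss to follow-up and withdrawal, nothing makes it the routine source for outcome 13, and its reference to a dose fits a pessary no better than an untreated woman.

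Symptoms may also reach the record through unscheduled visits (TO07), adverse event reports (TO12) and the final interview. None of these is described as asking every woman the same symptom questions. What remains is an unreconciled difference in wording that allows unequal collection.

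**Conclusion.** The point holds as a possible bias in one secondary tolerability outcome. Section 4.4 and Appendix A describe the same visit differently, and the section 4.4 version, taken literally in an unblinded trial, could lose background symptoms among usual-care women without progesterone. The direction would be against the pessary. For discharge, the inflation is at most from 3.39 to between 3.77 and 6.78 for an untreated share of 10% to 50%. That range rests on an assumed share, on complete loss in untreated women and none elsewhere, and on equal background rates with and without progesterone. At the low end the conclusion about discharge would be unchanged. Whether any loss would occur depends on the TO05 items, which cannot be checked here. The primary outcome, delivery or fetal demise before 37 weeks, does not depend on symptom reporting and is not affected.

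**What to change.** Reconcile section 4.4 with Appendix A:

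- State that one fixed symptom list (vaginal discharge, pelvic or vaginal discomfort, bleeding, other) is asked at the one-week call and at every monthly visit in both arms, and recorded whatever the treatment received or the judged cause.
- Define outcome 13 as any such symptom reported after randomization, compared by randomized arm.
- Keep relatedness as a separate item used for safety reporting.
- On TO11, count side effects from the last contact instead of the last dose.

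If TO05 already asks such a list of every woman, the form can stay and the protocol text should say so.

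The calls, visits and forms already exist, so the cost is wording in section 4.4, the definition of outcome 13, any needed changes to TO05 and TO11, and the Steering Committee and IRB approval that section 1.3 requires for a protocol change. The downside is a few more symptom entries in usual care, and recorded rates in both arms that include background symptoms. Reporting differences caused by giving symptom education only to pessary women would remain.

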3.2 Secondary Research Questions

Secondary research questions that this study will address are:

- Does treatment with the Arabin cervical pessary for women with a short cervix (≤ 20 mm) compared with usual care alter any of the secondary outcomes listed in Section 4.6, including:
 - Preterm birth less than 28 weeks, 32 weeks, or 35 weeks?
 - Neonatal morbidity or mortality?
 - Special care nursery admission?
 - Lower genital tract or urinary tract infection?
 - Physician interventions including labor inhibition, cerclage, and bed rest?
 - Alter the rates of inflammatory markers in cervicovaginal fluid?
- What is the acceptability of and compliance with the Arabin pessary as an adjunctive with vaginal progesterone?
- Are there specific subgroups in which treatment with the pessary is more efficacious? (See Section 5.5 for a discussion of subgroup analyses.)
-

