5.5 Analysis Plan

All statistical analyses will be based upon the total cohort of patients randomized into the trial. Although data on some patients may be missing, all relevant data available from each patient will be employed in the analyses. Patients will be included in the treatment group to which they were randomly assigned regardless of compliance.

The primary analysis will consist of a simple comparison of binomial proportions. The relative risk and confidence interval will be reported. The individual components of the composite outcome will also be examined. If the treatment groups are found to differ on a pre-treatment factor known to be a risk factor for the outcome, the statistical analysis will adjust for these differences. An evaluation of treatment by center interaction will be included. An analysis adjusting by center also will be performed to ensure that center differences do not change the conclusion.

If the two groups show a difference in the incidence of the primary outcome, interactions will be evaluated and subgroup analyses conducted to determine whether the effect prevails throughout particular subgroups of patients. Indeed, NIH guidelines require investigators to evaluate consistency between the genders and across racial subgroups (see Section 5.5.1). It should be noted, however, that subgroup analyses have been greatly abused, particularly when there is no overall treatment difference.³⁶ There is a strong temptation to search for a specific subpopulation in which the therapy is nevertheless effective. Yusuf et al. concluded "the overall 'average' result of a randomized clinical trial is usually a more reliable estimate of the treatment effect in the various subgroups examined than are the observed effects in individual subgroups."³⁷ Thus subgroup analyses will be interpreted with care.

It is generally acknowledged that subgroup analysis that is pre-specified in the protocol has more validity than ad-hoc comparisons. The following factors will be considered for subgroup analysis, if there is a significant interaction between the factor of interest and the treatment effect.

- Race/ethnicity (see below)
- Gestational age at randomization (< 20 weeks and \geq 20 weeks)
- Cervical length at randomization (< 15 and \geq 15 -20 mm)
- Treatment with vaginal progesterone (as planned per usual care locally)
- Screening to randomization interval
- Debris/funneling on randomization ultrasound
- Obesity by BMI category
- Parity

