- Bacterial vaginosis/Nugent score at enrollment—Nugent \geq 7 with pH > 4.4
- Prior cervical surgery including LOOP/ LEEP

Loss to follow-up will be defined as no information regarding pregnancy prior to 37 weeks. Those defined as lost to follow-up will not be included in the primary analysis. It is expected that the loss to follow-up rate will be very low. For trials conducted by the MFMU Network, the loss to follow-up rate has typically been under 2 percent. However, a sensitivity analysis will be performed including patients lost to follow-up with different assumptions regarding their outcome, to determine whether the results are robust.

Since many of the secondary endpoints are dichotomous variables like the primary outcome, standard statistical methods for rates and proportions will be appropriate. The Wilcoxon rank sum test will be used to compare continuous variables, and survival analysis methodology may be used to compare time-to-event variables.

In general, analyses of data will be conducted to address the primary and secondary research questions of the trial, and other interrelationships among elements of study data of interest to the investigators and of relevance to the objectives of the study.

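### No baseline-adjusted comparison is planned for the paired cervicovaginal samples, although adjusting for the pre-randomization value on a suitable scale would be more precise

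*Combined protocol and SAP*

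**What the plan says.** Section 3.2 lists among its secondary questions whether the pessary will "Alter the rates of inflammatory markers in cervicovaginal fluid".

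Section 4.1 provides the baseline measurement, taken just before randomization: "A cervicovaginal fluid sample, vaginal Gram stain, and vaginal pH will be collected to assess for local inflammation and vaginitis". Section 4.4 provides the follow-up measurement, conditionally: "A second set of cervicovaginal fluid samples will be collected if an in-person study visit occurs between 24 to 32 weeks". The same section gives the purpose of the pair, which is "to examine any potential interval changes that may be associated with the assigned treatment arm". It names no test or model.

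Section 5.5 supplies the only general method for continuous data: "The Wilcoxon rank sum test will be used to compare continuous variables". It foresees adjustment only after an imbalance has been seen: "If the treatment groups are found to differ on a pre-treatment factor known to be a risk factor for the outcome". The markers do not appear in the outcome lists of section 4.6. The plan gives no marker scale, SD or between-sample correlation, and no expected number of pairs.

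**The concern.** The trial collects a pre-randomization value of each marker, which is the natural covariate for the value at 24 to 32 weeks, but no planned analysis uses it that way. Read together, sections 4.4 and 5.5 leave two likely analyses: a rank sum test on the change, or a rank sum test on the second sample. The first carries the noise of both samples. The second discards the baseline.

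What is at stake is efficiency. Only women with both samples can contribute to a paired analysis, and their number is unknown, so a less precise method makes a real difference in markers easier to miss. The gap between samples also varies widely. Randomization runs from 16 weeks 0 days to 23 weeks 6 days and the second sample from 24 to 32 weeks, so the gap can be one day or 16 weeks. The stated methods take no account of this.

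**Working it through.** **Inputs.** The plan gives no figure for the marker comparison, so there is none to reproduce. Its 850 women (850/2 = 425 per arm) are sized for the primary outcome and only cap the number of pairs. These inputs are assumptions: correlation r from 0.2 to 0.8, an arm difference of 0.25 SD, and 200 pairs per arm in the simulation. Alpha is 5% two-sided, as in section 5.2.

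**Variances.** Let σ0 and σ1 be the SDs at the two times. The variance of the arm contrast is (2/n)·v, where v is:

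- change score: σ0² + σ1² - 2rσ0σ1
- second sample alone: σ1²
- analysis of covariance: σ1²(1 - r²)

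Change minus covariance equals (σ0 - rσ1)², which cannot be negative. So on a common scale and in large samples the change score is never the more precise, whatever the SDs. With both SDs equal to 1 the three values are 2(1-r), 1 and 1-r².

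**Women needed relative to covariance adjustment.** For the change score the ratio is 2(1-r)/(1-r²) = 2/(1+r). For the second sample alone it is 1/(1-r²).

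| r | Change score | Second sample alone |
|---|---|---|
| 0.3 | 2/1.3 = 1.54 | 1/0.91 = 1.10 |
| 0.5 | 2/1.5 = 1.33 | 1/0.75 = 1.33 |
| 0.7 | 2/1.7 = 1.18 | 1/0.51 = 1.96 |

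Below r=0.5 the change score is worse even than ignoring the baseline. Above r=0.5 ignoring the baseline is the worse choice.

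**Pairs per arm for 80% power at 0.25 SD.** n = 2(1.96+0.84)²·v/0.25², about 251·v before rounding up.

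| r | Change | Second sample | Covariance |
|---|---|---|---|
| 0.2 | 402 | 252 | 242 |
| 0.3 | 352 | 252 | 229 |
| 0.5 | 252 | 252 | 189 |
| 0.8 | 101 | 252 | 91 |

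**Simulation with the rank sum test itself** (2,000 runs, 200 pairs per arm, 0.25 SD, normal or log scale):

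| r | Rank sum on change | Rank sum on second sample | Covariance |
|---|---|---|---|
| 0.2 | 48% | 68% | 71% |
| 0.5 | 67% | 68% | 81% |
| 0.8 | 97% | 68% | 99% |

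**Dependence on scale.** For a strongly skewed marker (lognormal, log SD 1.5) left on its raw scale:

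| r | Rank sum on raw change | Linear covariance, raw values | Covariance on ranks |
|---|---|---|---|
| 0.2 | 45% | 33% | 70% |
| 0.5 | 62% | 36% | 80% |
| 0.8 | 94% | 54% | 97% |

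Untransformed linear adjustment loses to the rank sum test here. Adjustment on ranks does not.

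**The case against.** The strongest objection is that the plan never states the method being criticized. A reader might infer that it prescribes a rank sum test on marker change scores. It does not: section 4.4 expresses an interest in interval change, section 5.5 gives a general default, and nothing joins them. A baseline-adjusted model would also answer the question in section 4.4. This stands. The point therefore rests on the absence of any adjusted analysis and on the comparison with both likely unadjusted ones.

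Section 3.2 speaks of rates, which may mean a binary comparison. The variance formulas above would then not apply. This stands as a limit on the figures. However, the only cutoff given is for bacterial vaginosis as a subgroup factor (Nugent score and pH), with none for the inflammatory markers, so the analysis would still need to be specified.

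A reader might infer that adjustment costs nothing. The skewed-marker results show otherwise when values are left untransformed.

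A reader might also infer that a safety signal could be lost. The documents give this little support: chorioamnionitis, vaginal infection, antibiotic or antifungal use and neonatal infection are recorded directly, and adverse events go to the monitoring committee.

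Finally, adjustment does not cure selective availability of the second sample. Section 4.4 guarantees an in-person visit in one arm only: "Women randomized to pessary will have at least one in-person visit to undergo a digital examination". It does not say that this visit falls at 24 to 32 weeks, and women who have already delivered have no second sample. This stands, and affects any analysis of the pairs.

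**Conclusion.** The point holds as a modest improvement. The plan takes a pre-randomization marker value and does not plan to adjust for it. An adjusted comparison on a log or rank scale is more precise than either unadjusted reading for any r above 0 and below 1. Against the change score the gain is large at low correlation (54% more women needed at r=0.3) and small at high correlation (97% versus 99% simulated power at r=0.8). Against the second sample alone the pattern reverses.

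These sizes rest on an assumed correlation, equal SDs, a continuous marker and, for power, an assumed difference and number of pairs. The documents supply none of these.

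A reader might take this as a claim that the planned comparison is biased. It is not: with randomized arms the choice among these analyses affects precision only, and selective availability of second samples is a separate matter. The question is in effect exploratory, and the primary outcome is untouched.

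**What to change.** In section 5.5, state that:

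- continuous marker levels and pH at 24 to 32 weeks are compared between arms by analysis of covariance on a pre-specified log or rank scale, with the pre-randomization value and gestational age at randomization as covariates;
- Nugent score is analysed by a rank or ordinal model, and any dichotomized marker by a logistic model, with baseline status as a covariate in each;
- an estimate and confidence interval are reported, and interval change is given only as a descriptive summary;
- timing of the second sample enters a sensitivity analysis only, because it is determined after randomization and may differ by arm through visit pattern;
- the number of women with paired samples is reported by arm.

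The cost is a few lines of text, with no new samples or data. The one real demand is that the scale for each measure be fixed before analysis, since untransformed linear adjustment can lose power for strongly skewed markers.
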